Recruitment and enrollment into the study will occur on an ongoing basis, with each group being recruited and vaccinated in sequence.

48 subjects will be enrolled into 4 groups of 12:

[figure not shown]
Subjects will be enrolled sequentially and upon enrollment will be randomized to one of the following IP assignments in a double-blind fashion:

- Group 1 IP allocation (n=12 subjects):
  - 12 subjects will receive 100 $\mu$ g Na-GST-1/Alhydrogel® delivered by IM injection in the deltoid muscle.
- Group 2 IP allocation (n=12):
  - 12 subjects will receive Na-GST-1/Alhydrogel® plus 500 $\mu$ g CpG 10104 delivered by IM injection in the deltoid muscle.
- Group 3 IP allocation (n=12):

- 12 subjects will receive Na-GST-1/Alhydrogel® plus 5µg AP 10-701 delivered by IM injection in the deltoid muscle.
- Group 4 IP allocation (n=12):
  - 12 subjects will receive sterile saline delivered by IM injection in the deltoid muscle

**Estimated Time to Complete Enrollment:** 6 months

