10. Other condition that in the opinion of the investigator would jeopardize the safety or rights of a volunteer participating in the trial or would render the subject unable to comply with the protocol.
11. Planned participation in another investigational vaccine or drug trial within 30 days of starting this study or until the last study visit.

*This may include other licensed or unlicensed vaccines, drugs, biologics, devices, blood products, or medications.*

12. Volunteer has had medical, occupational, or family problems as a result of alcohol or illicit drug use during the past 24 months.

13. Positive fecal occult blood test at screening.
14. Infection with a pathogenic intestinal helminth as determined by stool examination for ova and parasites at screening.
15. History of iron deficiency anemia or laboratory evidence of iron deficiency (serum ferritin concentration below the lower reference limit).
16. History of hypoalbuminemia.
17. History of a severe allergic reaction or anaphylaxis.
18. Severe asthma as defined by the need for daily use of corticosteroid and/or long-acting beta agonist inhalers, or emergency clinic visit or hospitalization within 6 months of the volunteer's expected first vaccination in the study.
19. Positive test for hepatitis B surface antigen (HBsAg).
20. Positive confirmatory test for HIV infection.
21. Positive confirmatory test for hepatitis C virus (HCV) infection.
22. Using or intends to continue using oral or parenteral corticosteroids, high-dose inhaled corticosteroids (>800 µg/day of beclomethasone dipropionate or equivalent) or other immunosuppressive or cytotoxic drugs within 30 days of the volunteer's expected first vaccination in this study or planned use during the study.
23. Receipt of a live vaccine within 4 weeks or a killed vaccine within 2 weeks prior to the volunteer's expected first vaccination in the study.
24. Receipt of immunoglobulin or other blood products (with exception of Rho D immunoglobulin) within 90 days of the planned first study vaccination.
25. Known allergy to albendazole, amphotericin B or gentamicin.
26. History of previous infection with hookworm or continuous residence for more than 6 months in a community where hookworm is endemic.
27. Current or past scars, tattoos, or other disruptions of skin integrity at the intended site of larval application.
28. Previous receipt of the Na-GST-1/Alhydrogel® hookworm vaccine.
29. History of a surgical splenectomy.

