- c. The proportion of subjects with detectable hookworm eggs in each of the intervention groups (Groups 1, 2 and 3) will be compared to the proportion of subjects in the placebo control group (Group 4) using a one sided Fisher exact test. The p-values from the three tests will be adjusted using the Holm-Bonferroni procedure to control the familywise error rate at 0.05. Power calculations are based on this outcome.

Primary Objective #2: To evaluate the safety and reactogenicity of Na-GST-1/ Alhydrogel® delivered with or without AP 10-701 or CpG 10104 on Days 0, 56 and 112, in healthy, hookworm-naïve adults.

AEs will be coded according to Medical Dictionary of Regulatory Activities (MedDRA™) preferred terms. The frequency, severity, and relationship of AEs per each vaccine formulation of Na-GST-1 will be presented in tabular form using the MedDRA™ coded term and organized by MedDRA™ System, Organ, and Class (SOC) designations.

1. The frequency of solicited local injection site and systemic AEs, and unsolicited AEs will be summarized by SOC and preferred term.
2. Line listings of clinical and laboratory AEs classified as solicited injection site, solicited systemic, or unsolicited and will be displayed in tables stratified by formulation group (i.e., Na-GST-1/Alhydrogel, Na-GST-1/Alhydrogel plus AP 10-701, Na-GST-1/Alhydrogel plus CpG 10104, or saline placebo).
3. AEs will be summarized by severity and relationship to vaccine by individuals and formulation of Na-GST-1.
4. The frequency of vaccine-related SAEs and AESIs will be tallied as well as summarized by body system, by vaccine formulation.

*Primary Outcome #2 Measures:*

The following summary parameters will be evaluated for each formulation of Na-GST-1, in comparison to saline placebo control:

1. Frequency of solicited injection site and systemic reactogenicity, graded by severity, on the day of each study vaccination through 14 days after each study vaccination.
2. Frequency of solicited adverse events, graded by severity, on the day of CHHI through study Day 280.
3. Frequency of study vaccine-related Serious Adverse Events from the time of the first study vaccination through approximately 10 months after the last study vaccination.
4. Frequency of clinical safety laboratory adverse events.

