Secondary Objective #3: To assess the duration of antibody responses to Na-GST-1 induced by vaccination with Na-GST-1/Alhydrogel® delivered with or without AP 10-701 or CpG 10104.

*Secondary Outcome #2 and #3 Measures:*

The following parameters will be evaluated for each formulation of Na-GST-1, in comparison to the saline placebo control:

1. The anti-Na-GST-1 IgG antibody response, by a qualified indirect enzyme-linked immunosorbent assay (ELISA) at approximately 14 days after each vaccination, and approximately 1, 2, 4, 6, 7, 8 and 10 months after the third dose.

*Analysis Plan:*

- a. The proportion of participants with detectable anti-Na-GST-1 IgG responses will be summarized as a descriptive measure.
- b. IgG levels will be displayed graphically by study group using notched box plots at each time point.
- c. Geometric mean antibody responses will be compared between vaccine formulation groups at each time point. Comparisons between groups will be made by a one-way analysis of variance (ANOVA) with pair-wise comparisons between groups made by contrasts.
- d. Geometric mean antibody responses for each antigen will be compared using a regression model with main effects for the doses of Na-GST-1 (0 or 100µg), AP 10-701 (0 or 5 µg), and CpG 10104 (0 or 500µg).
- e. For antigen-specific log IgG levels, a three-way ANOVA will be conducted, with Na-GST-1, CpG 10104 and AP 10-701 doses as factors.
- f. Pair-wise comparisons of IgG levels on study Day 126 (2 weeks after the third vaccination) across all combinations of Na-GST-1 doses (i.e., 0 [placebo] or 100 µg), AP 10-701 doses (i.e., 0 or 5 µg), and CpG 10104 doses (0 or 500µg) will be assessed using Tukey's HSD.
- g. Percent change in IgG antibody levels from days of vaccination to days 7, 14 and 28 post-vaccination will be compared between vaccine formulation and dose groups. Values will be reported with 95% confidence intervals.
- h. Percent change in IgG antibody levels from vaccination day #1 to #2, from vaccination day #2 to #3, and from vaccination day #3 to day of CHHI will be compared between vaccine formulation and dose groups to assess the sustainability of the response from trough to trough and post-CHHI. Values will be reported with 95% confidence intervals.
- i. Percent change in IgG antibody levels from the peak following the third vaccination, to 1, 2, 4, 6, 7, 8 and 10 after the third vaccination. Values will be reported with 95% confidence intervals.

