#### 5.7.4.2 Secondary Endpoint Analysis

Fecal egg counts of the subjects in each of the vaccination (Groups 1, 2 and 3) and placebo (Group 4) groups will be assessed for normality. If normality assumption is confirmed, the comparison between vaccination groups (Group 1, 2 and 3) and placebo group (Group 4) will be done using T-test. Otherwise, the vaccination groups (Group 1, 2 and 3) will be compared with the placebo group (Group 4) using a Wilcoxon-Mann-Whitney rank-sum test. Continuous data will be summarized using the descriptive statistics (mean, median, minimum, maximum and median 95% CI). Mean or Median differences and corresponding 95% CIs will be computed for each pairwise comparison.

Time to patent infection (i.e., the first timepoint at which hookworm eggs are detectable in a fecal sample) will be displayed using Kaplan-Meier estimates, with log-rank tests used to compare the distribution of time-to-patency between groups and censoring of early withdrawals or those failing to develop patent infection.

The detectable anti-*Na-GST-1* IgG responses will be summarized as a descriptive measure using descriptive statistics (mean, standard deviation, median, minimum and maximum) for each observed measurement by vaccination groups and placebo. IgG levels will be displayed graphically by study group using time series and notched box plots at each time points.

Geometric mean antibody responses will be compared between vaccination groups and placebo at each time point using an ANOVA model. An ANOVA model will be fitted with IgG responses as the dependent variable and vaccination groups and placebo as independent variables. The estimated geometric least square means and geometric least square means difference from the model, 2-sided *p*-value and 95% CI for vaccination groups compared to placebo group will be constructed and presented for each time point.

Percent change in IgG antibody levels from days of vaccination to days 7, 14 and 28 post-vaccination, as well as percent change in IgG antibody levels from the peak following the third vaccination to 1, 2, 4, 6, 7, 8, and 10 months post-vaccination will be summarized using descriptive statistics (mean, standard deviation, median, minimum, maximum and 95% CI) for each observed measurement along with the percent change from baseline.

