A longitudinal model will be built to describe the IgG levels over time. Using a longitudinal panel model, differences in antibody isotype levels by vaccination groups and placebo will be explored. The analysis will take account of the correlation between measurements on the same subject. A mixed model repeated measure (MMRM) will be fitted with IgG levels as the dependent variable and vaccination groups and placebo, visits and interaction between groups and visits as independent variables. the estimated geometric means Standard Error and geometric means difference from the model, 2-sided *p*-value and 95% CI for vaccination groups and placebo will be constructed.

Logistic regression will be explored for the binary response of hookworm infection post-CHHI as a function of antibody response. Dependant variable will be the hookworm infection status (Positive/Negative) and independent variable will be the IgG responses and vaccination groups and placebo. Estimated number of subjects, Standard Error and odds ratio from the model, 2-sided *p*-value and Wald 95% CI for vaccination groups and placebo will be constructed.

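### The IgG ANOVA models pool one residual variance over saline and the three vaccine arms; if saline has almost no spread, each unadjusted adjuvant-versus-Alhydrogel contrast can be falsely positive in up to about 9% of trials instead of 5%

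*Protocol*

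**What the plan says.** Protocol 11.4, Secondary Outcomes #2 and #3, item c: "Comparisons between groups will be made by a one-way analysis of variance (ANOVA) with pair-wise comparisons between groups made by contrasts". The same section counts saline as a formulation group where it describes tables "stratified by formulation group (i.e., Na-GST-1/Alhydrogel, Na-GST-1/Alhydrogel plus AP 10-701, Na-GST-1/Alhydrogel plus CpG 10104, or saline placebo", so the one-way ANOVA is most naturally read as having four arms.

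Items d and e model the doses of Na-GST-1, AP 10-701 and CpG 10104. There are only four dose combinations, so an intercept and three dose effects reproduce the four group means, and the error term is that of the four-arm ANOVA. Item f takes the Day 126 pairs, with placebo as one combination; these "will be assessed using Tukey's HSD".

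SAP 5.7.4.2 follows the same line: "An ANOVA model will be fitted with IgG responses as the dependent variable and vaccination groups and placebo as independent variables". Its listed ANOVA output is limited: "95% CI for vaccination groups compared to placebo group will be constructed and presented for each time point". It adds a longitudinal model, "A mixed model repeated measure (MMRM) will be fitted with IgG levels as the dependent variable", without naming a covariance structure. SAP section 7 comments only on protocol item e.

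Both documents keep hypothesis 2, that adding AP 10-701 or CpG 10104 raises IgG over Na-GST-1/Alhydrogel alone. SAP 5.1 has a Shapiro-Wilk check that sends non-normal data to non-parametric tests. Nothing addresses unequal variance.

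**The concern.** An ANOVA contrast takes its standard error from the spread of every arm in the model, including arms outside the contrast. Saline contains no antigen, and exclusion criterion 26 bars anyone with "History of previous infection with hookworm or continuous residence for more than 6 months in a community where hookworm is endemic". Saline IgG should therefore sit near the floor of the assay, probably with little spread, while vaccinated participants vary in their response.

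A quarter of the error degrees of freedom would then come from an arm that carries little information on vaccine-arm variability. The pooled SD becomes too small for comparing one vaccine group with another, which is the comparison hypothesis 2 needs. With similar vaccine SDs it is too large for comparing a vaccine group with saline. A formulation could be credited with better immunogenicity by chance, in a trial meant to help choose between formulations. Analysing on the log scale does not remove the problem.

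**Working it through.** **Inputs from the documents.** "48 subjects will be enrolled into 4 groups of 12" (Protocol summary). Error df: 4 × 11 = 44, of which 33 come from the vaccine arms. Level 5% (Protocol 11.4), two-sided for IgG (SAP 5.7.4.2).

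**Inputs assumed.** Log scale, normal data, no true difference between vaccine arms. The saline/vaccine SD ratio r is not stated and is varied from 0 to 1. Vaccine-arm SDs are not stated; they are taken as equal first, then varied.

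**The plan's own figure.** For IgG this is only the nominal 5%. With all four SDs equal, simulation returns 5.0%.

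**Step 1: pooled variance.** With vaccine variance σ², E(MSE) = (3 + r²)σ²/4. At r = 0 this is 0.75σ². The SE of a vaccine-versus-vaccine contrast is then √0.75 = 0.866 of its true size.

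**Step 2: adjuvant versus Alhydrogel alone, r = 0.** The test statistic is distributed as T₃₃ × √(4/3) but is compared with t(0.975, 44) = 2.015. Rejection needs |T₃₃| > 2.015 × 0.866 = 1.745, which has probability 9.0%.

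**Step 3: less extreme saline spread (400,000 simulated trials per ratio).**

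| r | False-positive rate per unadjusted contrast |
|---|---|
| 0 | 9.0% |
| 0.1 | 9.0% |
| 0.25 | 8.7% |
| 0.5 | 7.7% |
| 0.75 | 6.3% |
| 1 | 5.0% |

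At r = 0, at least one of the two adjuvant contrasts rejects in 15.7% of trials, against 9.0% with equal variances.

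**Step 4: Day 126 Tukey, r = 0.** The critical value q(4, 44) = 3.776 is 3.776/√2 = 2.670 on the t scale. Rejection needs |T₃₃| > 2.670 × 0.866 = 2.312, or 2.7% per pair (1.1% with equal variances). Over the three vaccine pairs the simulated rate is 6.8% (2.8% with equal variances).

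**Step 5: vaccine versus saline, r = 0.** True variance is σ²/12; the model estimates 0.75σ² × 2/12 = 1.5σ²/12. The SE is √1.5 = 1.22 times too large. Non-coverage is P(|T₃₃| > 2.015 × 1.225 = 2.468) = 1.9%, so coverage is 98.1%. Against a Welch interval on about 11 df (t = 2.201), the width ratio is 1.225 × 2.015/2.201 = 1.12.

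**Step 6: unequal vaccine SDs, saline SD near 0.**

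| SDs: Alhydrogel / CpG / AP | CpG v Alhydrogel | AP v Alhydrogel | Non-coverage v saline, most variable arm |
|---|---|---|---|
| 0.5 / 1 / 1 | 6.6% | 6.6% | 4.1% |
| 1.5 / 1 / 1 | 11.4% | 11.5% | 6.0% |
| 1 / 1.5 / 1 | 11.4% | 4.7% | 6.0% |
| 1.5 / 0.8 / 0.8 | 12.9% | 12.9% | 8.7% |

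**Step 7: the SAP normality check.** Applied to ANOVA residuals (4,000 trials per ratio), it leaves 6.7% at r = 0, 7.8% at 0.1 and 8.1% at 0.25.

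**Step 8: alternatives.** With saline SD near 0, Welch contrasts give about 4.9% between vaccine groups and 4.9 to 5.0% non-coverage against saline. A pooled ANOVA on Groups 1-3 holds 5.0% only if their SDs are equal; it gives 3.4 to 7.9% where the Alhydrogel-alone SD differs from the other two.

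**The case against.** The strongest reply is that the size rests on two SDs the documents never give. Naivety and the absence of antigen make a low saline spread plausible but do not show it. On the log scale, values interpolated near an assay floor need not be tight, and no rule sets them to a single limit value. This stands, and so the rates are shown as a range.

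Nor does the scenario fit every visit. Protocol 2.1.6 reports antibody in the US trial after the second and third doses, so at Day 14 the vaccine arms may also be near the floor. Six of the ten listed IgG time points (2, 4, 6, 7, 8 and 10 months after dose 3) follow the larval challenge, when saline spread is unknown. The fit is clearest at Days 70, 126 and 140.

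The SAP's listed ANOVA output covers only vaccine versus placebo, where the error with similar vaccine SDs is conservative. That is true of the output. But SAP section 7 does not withdraw protocol items c, d or f, and the SAP keeps hypothesis 2, so the affected contrasts are still needed. Item c could be read as a three-arm ANOVA, but that would contradict the protocol's own count of formulation groups and the SAP model.

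The normality check gives partial protection only, because it does not test equality of variance. For the MMRM, a common variance across arms is only the default reading. Finally, these are secondary analyses in a study that seeks an indication of large effects.

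**Conclusion.** The point holds conditionally. Pooling without any provision for unequal variance is in the text, and unequal variance is foreseeable at Days 70, 126 and 140. If the vaccine SDs are similar, the false-positive rate per unadjusted adjuvant contrast is 7.7 to 9.0% for any saline SD up to half the vaccine SD.

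A reader might infer that these contrasts are wrong 9% of the time at every visit, and that intervals against saline are always too wide. The documents support neither. The 9% needs near-zero saline spread and similar vaccine SDs, and it does not describe the Day 126 Tukey comparisons. With unequal vaccine SDs the error can go either way, including intervals against saline that are too narrow. That unpredictability is itself a reason not to pool.

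The change is worth making before the analysis. It does not affect the primary efficacy conclusion.

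**What to change.** In Protocol 11.4 items c to f and SAP 5.7.4.2:

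- Use Welch-type contrasts (arm-specific variances, Satterthwaite df) on log IgG for Group 2 v 1, Group 3 v 1 and each vaccine group v saline.
- List Group 2 v 1 and Group 3 v 1 in the SAP output.
- Replace Tukey's HSD at Day 126 with an unequal-variance version such as Games-Howell.
- If all saline values lie at the assay limit, that arm's variance cannot usefully be estimated. Fit Groups 1-3 only, with separate variances, for the formulation contrasts. Dropping saline but still pooling is not enough (Step 8).
- In the MMRM, let the residual variance differ by group under a parsimonious covariance structure, or fit Groups 1-3 only. An unstructured matrix over the 16 scheduled antibody visits would need 16 × 17/2 = 136 parameters per arm from 12 participants.

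Cost: SAP wording, and error df for a formulation contrast falling from 44 to about 22 (12 + 12 − 2).

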## 3.2 Study Outcome Measures

### 3.2.1 Primary Outcome Measures

#### Efficacy

The following parameters will be evaluated for each formulation of Na-GST-1, in comparison to the saline placebo control:

1. Proportion of subjects with detectable hookworm eggs, at any time point, in fecal samples, as determined by microscopy using the qualified saline flotation technique.

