- j. Percent change in IgG antibody levels from the day of CHHI to 1, 3, 5, 6, 7 and 9 months post-CHHI. Values will be reported with 95% confidence intervals.
- k. A longitudinal model will be built to describe the IgG levels over time. Using a longitudinal panel model, differences in antibody isotype levels by formulation of Na-GST-1 will be explored. This will be accomplished using Proc Mixed in SAS 9.3 so the analysis will take account of the correlation between measurements on the same subject.
- l. Logistic regression will be explored for the binary response of hookworm infection post-CHHI as a function of antibody response, and a Poisson regression of the event counts (i.e., infection) as a function of IgG antibody response. In these models, vaccination group will be a covariate, rather than just using the IgG responses.

**Exploratory Objective #1:** To assess the relationship between the functional capacity of vaccine-induced antibodies that neutralize the *in vitro* activity of native Na-GST-1 enzyme and responses to CHHI in healthy, hookworm-naïve adults.

*Exploratory Outcome #1 Measure:*

The following parameters will be evaluated for each formulation of Na-GST-1, in comparison to the saline placebo control:

1. The functional capacity of vaccine-induced antibodies to neutralize the *in vitro* activity of the native Na-GST-1 enzyme.

*Analysis Plan:*

- a. Percent inhibition of native enzyme activity will be displayed graphically for the various study groups at each time point.
- b. Three-way ANOVAs with Na-GST-1, CpG 10104, and AP 10-701 as factors and percent inhibition as the outcome will be estimated.
- c. A longitudinal model will be built to describe percent inhibition of native enzyme activity over time. Using a longitudinal panel model, differences in percent inhibition by formulation of Na-GST-1 will be explored. This will be accomplished using Proc Mixed in SAS 9.3, so the analysis will take account of the correlation between measurements on the same subject.

**Exploratory Objective #2:** To compare the impact of vaccination with Na-GST-1/Alhydrogel® delivered with or without AP 10-701 or CpG 10104 on levels of hookworm DNA as detected by real-time PCR in healthy, hookworm-naïve adults challenged with CHHI.

*Exploratory Outcome #2 Measure:*

The following parameters will be evaluated for each formulation of Na-GST-1, in comparison to the saline placebo control:

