**Analysis Plan:**

- a. Antibody affinity will be displayed graphically for the various study groups at each time point post-vaccination and post-CHHI.
- b. Three-way ANOVAs with Na-GST-1, CpG 10104 and AP 10-701 as factors and overall affinity as the outcome will be estimated.
- c. A longitudinal model will be built to describe increasing antibody affinity (affinity maturation) over time. Using a longitudinal panel model, differences in affinity maturation by formulation of Na-GST-1 will be explored. This will be accomplished using Proc Mixed in SAS 9.3, so the analysis will take account of the correlation between measurements on the same subject.
- d. Logistic regression will be explored for the binary response of hookworm infection post-CHHI as a function of antibody affinity, and a Poisson regression of the event counts (i.e., infection) as a function of IgG antibody affinity. In these models, vaccination group will be a covariate, rather than just using the IgG affinity.

**Exploratory Objective #4:** To assess the relationship between Na-GST-1 specific memory B cells induced by vaccination with Na-GST-1/Alhydrogel® delivered with or without AP 10-701 or CpG 10104 and responses to CHHI in healthy, hookworm-naïve adults, as determined by the presence of eggs using a qualified flotation technique.

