**Analysis Plan:**

- a. The amount of Na-GST-1 specific memory B cells will be expressed as a percentage of total lymphocytes present in the blood.
- b. The percentage of specific memory B cells will be displayed graphically by study group at each time point.
- c. Two separate longitudinal panel analyses will test the null hypothesis that average percentages for each of memory B cells are the same in the different Na-GST-1 formulation groups over time. This will be accomplished using Proc Mixed in SAS 9.3

so the analysis will take account of the correlation between measurements on the same subject.

- d. Wilcoxon-Mann-Whitney tests will assess the null hypothesis that memory B cell levels are the same in the groups at the primary time point of Day 126, two weeks after final vaccination.
- e. Logistic regression will be explored for the binary response of hookworm infection post-CHHI as a function of memory B cell production, and a Poisson regression of the event counts (i.e., infection) as a function of memory B cell counts. In these models, vaccination group will be a covariate, rather than just using the B cell counts.

Exploratory Objective #5 To assess the relationship between innate immune responses to Na-GST-1/Alhydrogel® delivered with or without AP 10-701 or CpG 10104 and responses to CHHI in healthy, hookworm-naïve adults.

*Exploratory Outcome #5 Measure:*

The following parameters will be evaluated for each formulation of Na-GST-1, in comparison to the saline placebo control:

- 1. Innate immune responses on days of vaccination approximately 7 and 14 days following each vaccination; on day of CHHI; and then 7 and 14 days, and 5, 7, 13, and 20 weeks post-CHHI.

*Analysis Plan:*

- a. Changes in innate immune responses will be described using descriptive statistics.

A longitudinal panel analysis will test the null hypothesis that innate immune responses are the same among the different formulations of Na-GST-1 and examine for trends over time.

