#### Secondary:

1. To compare the impact of vaccination with *Na*-GST-1/Alhydrogel® delivered with or without AP 10-701 or CpG 10104 on fecal egg counts, as determined by the McMaster method, after controlled human hookworm infection (CHHI) with *N. americanus* larvae in healthy, hookworm-naïve adults.
2. To assess the relationship between antibody responses to *Na*-GST-1 induced by vaccination with *Na*-GST-1/Alhydrogel® delivered with or without AP 10-701 or CpG 10104 and responses to CHHI in healthy, hookworm-naïve adults, as determined by the presence of eggs using a qualified flotation technique.
3. To assess the duration of antibody responses to *Na*-GST-1 induced by vaccination with *Na*-GST-1/Alhydrogel® delivered with or without AP 10-701 or CpG 10104.
4. To assess the impact of vaccination with *Na*-GST-1/Alhydrogel® delivered with or without AP 10-701 or CpG 10104 on the affinity of antibody-antigen interactions, and how affinity relates to responses to CHHI in healthy, hookworm-naïve adults, as determined by the presence of eggs using a qualified flotation technique.
5. To assess the relationship between *Na*-GST-1 specific memory B cells induced by vaccination with *Na*-GST-1/Alhydrogel® delivered with or without AP 10-701 or CpG 10104 and responses

to CHHI in healthy, hookworm-naïve adults, as determined by the presence of eggs using a qualified flotation technique.

6. To assess the relationship between innate immune responses to *Na*-GST-1/Alhydrogel® delivered with or without AP 10-701 or CpG 10104 and responses to CHHI in healthy, hookworm-naïve adults.

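### The protocol's extra Poisson regressions of yes/no infection on immune markers have standard errors that are too large unless a robust variance is specified; the planned logistic models do not share the fault.

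*Protocol*

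**What the plan says.** Protocol 11.4 relates immune markers to infection in three places, each time with two models in one sentence.

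- IgG (Secondary Objectives #2 and #3, Analysis Plan item l). First comes the logistic model: "Logistic regression will be explored for the binary response of hookworm infection post-CHHI as a function of antibody response". Then comes "a Poisson regression of the event counts (i.e., infection) as a function of IgG antibody response". In both, "vaccination group will be a covariate, rather than just using the IgG responses".
- Affinity (Exploratory Objective #3, item d). Logistic again, then "a Poisson regression of the event counts (i.e., infection) as a function of IgG antibody affinity".
- Memory B cells (Exploratory Objective #4, item e). Logistic again, then "a Poisson regression of the event counts (i.e., infection) as a function of memory B cell counts".

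The infection outcome is binary for each subject. Protocol 3.2.1 defines it as "Proportion of subjects with detectable hookworm eggs, at any time point, in fecal samples", by flotation microscopy. No variance estimator is named for the Poisson models, and nothing says which model governs if the two disagree.

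SAP 5.7.4.2 keeps one infection model, a logistic regression on IgG: "Dependant variable will be the hookworm infection status (Positive/Negative". It contains no Poisson regression. SAP Section 7, which lists changes from the protocol, does not mention the removal. SAP 2.1 lists affinity ("on the affinity of antibody-antigen interactions, and how affinity relates to responses to CHHI") and memory B cells as secondary objectives 4 and 5, but the SAP gives no model for either.

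**The concern.** A Poisson model sets the variance of the outcome equal to its mean, p. A yes/no outcome has variance p(1−p), which is smaller. Unless a robust variance is requested, the standard error, interval and p-value for the marker are therefore all too wide or too large, and more so where infection is common. The protocol expects 90% infection in placebo.

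The protocol says in 2.2.1 that no immune correlate of protection is known, and it wants to learn how the immune responses relate to the effect on challenge. With 48 subjects, a test that almost never rejects, reported beside a valid one with no rule between them, invites a mistaken reading that a marker is unrelated to infection.

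**Working it through.** **Inputs from the documents.** 48 subjects, 12 per group; 90% infected expected in placebo and under 20% in at least one vaccine group (protocol 11.2); group as covariate (11.4); 5% significance level, taken here as two-sided for the slopes.

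**Assumed, because the documents give no value.** The marker slope (log odds per within-group SD of −1.0, −1.5 or −2.5) and the full set of group infection rates.

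**The plan's own figure.** The documents state no power for these regressions. The nearest stated figure is for the primary comparison: 87.7% at 90% v 20% infected and 73.2% at 90% v 30%. Exact enumeration of a one-sided Fisher test, 12 v 12 at 0.05/3, gives 88.8% and 74.1%. Both are within about one point, so the expected rates are consistent with the plan.

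**Step 1: standard error.** With M = diag(p), the model-based variance of the Poisson coefficients is (X′MX)⁻¹. The correct variance puts X′diag(p(1−p))X between two copies of that matrix. With a common p, the ratio of the two standard errors is r = 1/√(1−p):

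- p = 0.2: 1/√0.8 = 1.12
- p = 0.5: 1/√0.5 = 1.41
- p = 0.9: 1/√0.1 = 3.16

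**Step 2: size implied by r.** True size ≈ 2[1 − Φ(1.96r)].

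- r = 1.41: 1.96 × 1.41 = 2.77, size about 0.5%
- r = 1.75 (simulated median ratio for rates 50/20/20/90): 1.96 × 1.75 = 3.43, size about 0.1%
- r = 3.16: 1.96 × 3.16 = 6.2, size effectively zero

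**Step 3: simulation.** 1,500 trials per row, group as covariate. Entries are % of trials rejecting at 5% two-sided; rows with slope 0 show size.

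| Infected %, groups 1/2/3/placebo | Slope | Poisson, default | Poisson, sandwich | Logistic, Wald | Logistic, likelihood ratio |
|---|---|---|---|---|---|
| 50/20/20/90 | 0 | 0.1 | 6.8 | 4.5 | 7.3 |
| | −1.0 | 16.9 | 67.9 | 62.5 | 71.7 |
| | −2.5 | 71.7 | 98.4 | 88.3 | 97.3 |
| 70/50/50/90 | 0 | 0.1 | 7.3 | 5.1 | 7.6 |
| | −1.0 | 13.3 | 76.2 | 71.6 | 78.7 |
| | −2.5 | 72.6 | 100 | 96.3 | 99.5 |
| 30/20/20/90 | 0 | 0.1 | 6.5 | 4.9 | 7.3 |
| | −1.0 | 15.2 | 64.3 | 58.1 | 68.8 |
| | −2.5 | 74.4 | 97.2 | 86.7 | 96.9 |
| 90/90/20/90 | 0 | 0.0 | 4.7 | 3.3 | 7.1 |
| | −1.0 | 0.5 | 41.8 | 37.4 | 56.9 |
| | −2.5 | 7.6 | 83.4 | 59.4 | 91.9 |

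At −1.5, default Poisson gives 37–41% against 83–95% for logistic Wald in the first three settings, and 1.3% against 56.8% in the fourth.

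Other vaccine-group rate sets (all 50%; 70/50/30%; 80/70/60%), with placebo at 90% and slope −1.0, gave 4–30% for default Poisson against 71–83% for the logistic likelihood-ratio test. The highest true size found for default Poisson in any run was 0.5%.

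**The case against.** **Logistic regression comes first in every one of these sentences.** This stands. A reader might infer that the whole search for a correlate of protection loses most of its power. The documents do not support that: a suitable model for a binary outcome is planned for all three markers, and its power is not touched. The loss belongs to the companion model.

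**The SAP has already dropped the Poisson model for IgG.** This stands too. Protocol 11.4 defers the full methods to a later analysis plan, and that plan uses logistic alone. For affinity and memory B cells the SAP is silent, so the protocol's paired sentences remain the only plan. The SAP cites protocol Version 4.0, while the protocol reviewed carries a 2025 approval date. If the versions differ, that could explain the silence in Section 7, but the current texts still need to be aligned.

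**The regressions are exploratory in nature, and a sandwich variance is not excluded.** Both are true. No power is claimed for them, and the fault is an omitted specification. However, an analyst following the text would normally get the default variance.

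**The phrase might mean egg counts.** A reader might infer this and expect false positives from overdispersion. The text does not support it: the parenthesis defines the event as infection, the objectives specify presence of eggs by flotation, and egg counts have their own rank-sum analysis under Secondary Objective #1.

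**The slope is assumed.** This stands. At −2.5 in the three settings with lower infection rates, default Poisson reaches 72–74% against 87–96% for logistic Wald, so the loss is not always large.

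**Conclusion.** The point holds for the additional Poisson models under default variance. Their standard errors are inflated by about 1.4-fold at 50% infected and about 3-fold at 90%, and their true size is about 0–0.5% instead of 5%. At an assumed log odds of −1 per SD, their power is roughly 4–30% against about 58–83% for logistic in most settings, and 0.5% against 37% when three groups are 90% infected. The standard-error result is algebra and does not depend on the slope; the power figures do, and on the assumed rates.

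The error is conservative, so it would not create a false correlate. The harm is a misleading null beside a valid result: in one set of runs at slope −1.0, logistic was significant and Poisson was not in 58–69% of trials. The remaining exposure is mainly affinity and memory B cells. This is a correction to make before analysis, not a flaw in the design.

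**What to change.** 1. In protocol 11.4, delete the Poisson clause from item l (IgG), item d (affinity) and item e (memory B cells), and rely on the logistic model already planned.
2. If a relative risk is wanted, keep the clause as a modified Poisson model with sandwich variance and a small-sample t reference, and label it supplementary.
3. State that the logistic model governs the conclusion.
4. Record the removal of the Poisson model in SAP Section 7.
5. Add the logistic models for affinity and memory B cells to SAP 5.7.4.2. Do not carry Poisson wording back into the SAP for IgG.

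The cost is a few lines of text, with no change to data collection or sample size. Deletion gives up a direct relative-risk estimate. The sandwich option has a size of about 4–7% with 48 subjects, slightly above nominal in most settings, and here it had no power advantage over the logistic likelihood-ratio test except marginally at the steepest slope. When writing the logistic models, note that the Wald test weakens at steep slopes with high infection (59.4% against 91.9% for likelihood ratio in the last row of the table), while the likelihood-ratio test runs at 7.1–7.6%. The choice between them should be stated.
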